13 APPENDIX 1 CALCULATION OF SYNTAX SCORES

First assess dominance coronary system (Left/Right dominance) of the treated vessel.

If left dominance, treated vessel segment:

- RCA
 - RCA proximal 1 [+0]
 - RCA mid 2 [+0]
 - RCA distal 3 [+0]
- LM Left main 5 [+6]
- LAD
 - LAD proximal 6 [+3.5]
 - LAD mid 7 [+2.5]
 - LAD apical 8 [+1]
 - First diagonal 9 [+1]
 - Add. first diagonal 9a [+1]
 - Second diagonal 10 [+0.5]
 - Add. second diagonal 10a [+0.5]
- LCX
 - Proximal circumflex 11 [+2.5]
 - Intermediate/anterolateral 12 [+1]
 - First obtuse marginal 12a [+1]
 - Add. second obtuse marginal 12b [+1]
 - Distal circumflex 13 [+1.5]
 - Left posterolateral 14 [+1]
 - Add. first left posterolateral 14a [+1]
 - Add. second left posterolateral 14b [+1]
 - Posterior descending 15 [+1]

[figure not shown]

Document ID:	<As applicable, per local requirements>	Document title:	Classification:	For internal use
Modified:	11MAY2023	Statistical Analysis Plan		
Version:	3.0	Template ID:	ClinicalStudyTemplate0025	Approver:
Status:	Final	Template Version Date:	02MAR2018	Page: 47 of 52

Statistical Analysis Plan

If right dominance, treated vessel segment:

RCA	
o RCA proximal	1 [+1]
o RCA mid	2 [+1]
o RCA distal	3 [+1]
o Posterior descending	4 [+1]
o Posterolateral from RCA	16 [+0.5]
o First posterolateral from RCA	16a [+0.5]
o Second posterolateral from RCA	16b [+0.5]
o Third posterolateral from RCA	16c [+0.5]
LM Left main	5 [+5]
LAD	
o LAD proximal	6 [+3.5]
o LAD mid	7 [+2.5]
o LAD apical	8 [+1]
o First diagonal	9 [+1]
o Add. first diagonal	9a [+1]
o Second diagonal	10 [+0.5]
o Add. second diagonal	10a [+0.5]
LCX	
o Proximal circumflex	11 [+1.5]
o Intermediate/anterolateral	12 [+1]
o Obtuse marginal	12a [+1]
o Obtuse marginal	12b [+1]
o Distal circumflex	13 [+0.5]
o Left posterolateral	14 [+0.5]
o Left posterolateral	14a [+0.5]
o Left posterolateral	14b [+0.5]

Significant lesion (diameter stenosis >50%)? Y/N [Y: diseased segment score x2]

If RCA proximal (1), Left main (5), LAD proximal (6) or LCX proximal circumflex (11), Aorto-ostial stenosis? [Y: +1]

Total occlusion? Y/N (Y: diseased segment score x5)

Document ID:	<As applicable, per local requirements>	Document title:		Classification:	For internal use
		Statistical Analysis Plan			
Modified:	11MAY2023			Author:	
Version:	3.0	Template ID:	ClinicalStudyTemplate0025	Approver:	
Status:	Final	Template Version Date:	02MAR2018	Page:	48 of 52

Statistical Analysis Plan

If, total occlusion

- Age >3 months or unknown [+1]
- Blunt stump [+1]
- Bridging [+1]
- Side branch
 - Yes, all sidebranches <1.5mm [+1]
 - Yes, both sidebranches <1.5mm and ≥1.5mm are involved [+1]

Trifurcation? Y/N

If yes, specify:

- 1 diseased segment involved [+3]
- 2 diseased segments involved [+4]
- 3 diseased segments involved [+5]
- 4 diseased segments involved [+6]

Bifurcation? Y/N

If yes, specify type of bifurcation lesion:

- Medina 1,0,0 [+1]
- Medina 0,1,0 [+1]
- Medina 1,1,0 [+1]
- Medina 1,1,1 [+2]
- Medina 0,0,1 [+2]
- Medina 1,0,1 [+2]
- Medina 0,1,1 [+2]

If bifurcation, bifurcation angulation (between distal main vessel and side branch) < 70°? [Y: +1]

Severe tortuosity? Y/N [Y: +2]

Length >20mm? Y/N [Y: +1]

Document ID:	<As applicable, per local requirements>	Document title:		Classification:	For internal use
		Statistical Analysis Plan			
Modified:	11MAY2023			Author:	
Version:	3.0	Template ID:	ClinicalStudyTemplate0025	Approver:	
Status:	Final	Template Version Date:	02MAR2018	Page:	49 of 52

Statistical Analysis Plan

Heavy calcification? Y/N [Y: +2]

Thrombus? Y/N [Y: +1]

Diffusely diseased and narrowed segment? Y/N [Y: +1 per segment]

If yes, specify

- LAD proximal 6
- LAD mid 7
- LAD apical 8
- First diagonal 9
- Add. first diagonal 9a
- Second diagonal 10
- Add. second diagonal 10a

SYNTAX score per vessel: Add the above scored points.

Overall SYNTAX Score per patient: Take the maximum of the scored points across the vessels.

Document ID:	<As applicable, per local requirements>	Document title:	Classification:	For internal use
Modified:	11MAY2023	Statistical Analysis Plan		
Version:	3.0	Template ID:	ClinicalStudyTemplate0025	Approver:
Status:	Final	Template Version Date:	02MAR2018	Page: 50 of 52

Statistical Analysis Plan**Document Revision History**

Version	Date	Author	Reason for Change
Final 1.0	03FEB2020	[REDACTED]	NA
Final 2.0	14MAR2023	[REDACTED]	Updated definition of FAP, updated cut-off points for CKD classification, updated definition of overall syntax score, used tertiles of the SYNTAX score as index of complexity of PCI procedure, added subgroup analysis of roadmap quality, updated list of TLFs, minor textual changes.
Final 3.0	11MAY2023	[REDACTED]	Added total occlusion to calculation of SYNTAX score in Appendix1, added analysis populations to summary of changes from the protocol.

Document ID:	<As applicable, per local requirements>	Document title:	Classification:	For internal use
Modified:	11MAY2023	Statistical Analysis Plan		

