Step 1 Dominance: determine right or left coronary artery dominance

Step 2 Coronary segment: each diseased coronary segment is assigned a weight depending on its location

Segment No	Right dominance	Left dominance
1 RCA proximal	1	0
2 RCA mid	1	0
3 RCA distal	1	0
4 Posterior descending artery	1	n.a.
16 Posterolateral branch from RCA	0.5	n.a.
16a Posterolateral branch from RCA	0.5	n.a.
16b Posterolateral branch from RCA	0.5	n.a.
16c Posterolateral branch from RCA	0.5	n.a.
5 Left Main	5	6
6 LAD proximal	3.5	3.5
7 LAD mid	2.5	2.5
8 LAD apical	1	1
9 First diagonal	1	1
9a First diagonal ^a	1	1
10 Second diagonal	0.5	0.5
10a Second diagonal ^a	0.5	0.5
11 Proximal circumflex artery	1.5	2.5
12 Intermediate/ anterolateral artery	1	1
12a Obtuse marginal ^a	1	1
12b Obtuse marginal ^b	1	1
13 Distal circumflex artery	0.5	1.5
14 Left posterolateral	0.5	1
14a Left posterolateral ^a	0.5	1
14b Left posterolateral ^b	0.5	1
15 Posterior descending	n.a.	1

Document ID:	<As applicable, per local requirements>	Document title:		Classification:	For internal use
		Statistical Analysis Plan			
Modified:	11MAY2023	Template ID:	ClinicalStudyTemplate0025	Author:	
Version:	3.0	Template Version Date:	02MAR2018	Approver:	
Status:	Final			Page:	19 of 52

Statistical Analysis Plan

Step 3	Diameter stenosis	
The score of each diseased coronary segment is multiplied by two in case of a stenosis 50-99% and by five in case of total occlusion.
 
In case of total occlusion, additional points will be added as follows:
 
 - Age >3 months or unknown +1 - Blunt stump +1 - Bridging +1 - First segment visible distally +1 per non-visible segment - Side branch at the occlusion +1 if <1.5 mm diameter +1 if both <1.5 mm and >1.5 mm diameter +0 if ≥1.5 mm diameter (i.e. bifurcation lesion)
Step 4	Trifurcation lesion	
The presence of a trifurcation lesion adds additional points based on the number of diseased segments:
 
 - 1 segment +3 - 2 segments +4 - 3 segments +5 - 4 segments +6
Step 5	Bifurcation lesion	
The presence of a bifurcation lesion adds additional points based on the type of bifurcation according to the Medina classification:126
 
 - Medina 1,0,0-1,0-1,0 +1 - Medina 1,1,1-0,0,1-1,0,1-0,1,1 +2 
Moreover, the presence of a bifurcation angle <70° adds one additional point

Step 6	Aorto-ostial lesion	The presence of aorto-ostial lesion segments adds one additional point

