Step 7	Severe tortuosity	The presence of severe tortuosity proximal of the diseased segment adds two additional points
Step 8	Lesion length	Lesion length >20 mm adds one additional point
Step 9	Calcification	The presence of heavy calcification adds two additional points
Step 10	Thrombus	The presence of thrombus adds one additional point
Step 11	Diffuse disease/ small vessels	The presence of diffusely diseased and narrowed segments distal to the lesion (i.e. when at least 75% of the length of the segment distal to the lesion has a vessel diameter <2 mm) adds one point per segment number

SYNTAX: Synergy between Percutaneous Coronary Intervention with TAXUS and Cardiac Surgery

Figure 1 Steps to determine SYNTAX score as an index for anatomical complexity of the PCI [from Neumann 2018]

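### The SAP's two SYNTAX scoring rules, in Section 6 and Appendix 1, conflict on total occlusion and diffuse disease, and neither is said to govern

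*SAP*

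**What the plan says.** SAP Section 6 (Definitions) sends the reader both to its figure and to Appendix 1 for the SYNTAX score, and gives neither precedence.

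- **Stenosis and occlusion, Section 6, Step 3:** "The score of each diseased coronary segment is multiplied by two in case of a stenosis 50-99% and by five in case of total occlusion". Protocol Section 7.5, Figure 4, has the same rule.
- **Stenosis and occlusion, Appendix 1:** two separate yes/no items, "Significant lesion (diameter stenosis >50%)? Y/N [Y: diseased segment score x2" and, later, "Total occlusion? Y/N (Y: diseased segment score x5". The closing instruction is "SYNTAX score per vessel: Add the above scored points".
- **Extra occlusion points, Section 6:** these include "First segment visible distally +1 per non-visible segment". Appendix 1 carries the other occlusion items but not this one.
- **Diffuse disease, Section 6, Step 11:** each affected segment "adds one point per segment number", with no restriction by vessel.
- **Diffuse disease, Appendix 1:** "Diffusely diseased and narrowed segment? Y/N [Y: +1 per segment", followed by a list to choose from that holds segments 6, 7, 8, 9, 9a, 10 and 10a only.

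The patient's score is the maximum over treated vessels and is cut into tertiles. It is used in SAP Sections 8.10 (procedure characteristics), 8.11.3.3 and 8.13 (complexity subgroups), and 4.5 and 8.14 (intervention difficulty as a possible covariate). The revision history shows that Version 3.0 added total occlusion to Appendix 1. Section 9.2, which lists departures from the protocol analysis, mentions the tertiles but no change to the scoring items.

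**The concern.** Two programmers working from this SAP could give the same patient different scores. In Appendix 1 a complete occlusion satisfies both the x2 item, which has no 99% ceiling, and the x5 item, and nothing says that one displaces the other. The missing non-visible-segment item pulls occlusion scores down. The LAD-only list makes a diffuse-disease point depend on which vessel was treated, for a reason that is not part of the Section 6 score.

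Because the patient score is a maximum over vessels, one mis-scored vessel can set it. At stake are the membership of the three complexity groups, each tested one-sided at 2.5%, the descriptive SYNTAX tables, and any sensitivity analysis that uses the score as a covariate.

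**Working it through.** The plan states no figure that depends on this point, so there is nothing to reproduce. The check compares the two rules item by item.

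**1. Segment weights.** All weights in the Section 6 table and Appendix 1 agree, for right and left dominance. The conflict lies only in the multipliers and the added items.

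**2. Multiplier for a total occlusion.** Let w be the segment weight. Section 6 gives 5w. Appendix 1 allows three readings:

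- x5 replaces x2: 5w, excess 0
- both are added: 2w + 5w = 7w, excess 2w
- they compound: 2 × 5 × w = 10w, excess 5w

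| Segment (weight) | Section 6 | Replace | Add | Compound |
|---|---|---|---|---|
| Left main, right dominance (5) | 25 | 25 | 35 | 50 |
| LAD proximal (3.5) | 17.5 | 17.5 | 24.5 | 35 |
| RCA proximal, right dominance (1) | 5 | 5 | 7 | 10 |
| Second diagonal (0.5) | 2.5 | 2.5 | 3.5 | 5 |
| RCA, left dominance (0) | 0 | 0 | 0 | 0 |

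The compound reading fits least well with an instruction to add points.

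**3. The omitted item.** If k segments are non-visible, Section 6 adds k and Appendix 1 adds nothing. The net difference (Appendix 1 minus Section 6) is (m − 5)w − k, with m = 5, 7 or 10.

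- w = 3.5, k = 1: −1 (replace), 7 − 1 = +6 (add), 17.5 − 1 = +16.5 (compound).
- w = 0.5, k = 1, add: 1 − 1 = 0.
- w = 0, or the replace reading: −k, so the occlusion is under-scored.

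The sign is therefore not fixed.

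**4. Diffuse disease.** Section 6 lists 25 distinct segments across the two dominances and Appendix 1 offers 7, so 25 − 7 = 18 have no entry. Each affected segment among those 18 loses 1 point relative to Section 6.

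**5. Boundary.** Section 6 includes a stenosis of exactly 50%; Appendix 1 requires more than 50%.

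**6. Effect on tertiles, illustration only.** The documents give no prevalence of total occlusion or diffuse disease, so every rate here is an assumption. A simulation took 394 patients with one right-dominant lesion each, 46% of them in LAD or diagonal segments. Occluded lesions had 0 to 2 non-visible segments, and diffuse disease affected one or two segments. It compared tertile membership under the two rules.

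- Occlusion in 1% to 10% of patients, across the three readings and with the omitted item included: about 0.3% to 3.8% change tertile (394 × 0.003 ≈ 1 to 394 × 0.038 ≈ 15 patients).
- Diffuse disease in 2% to 20%, scored only in the LAD: about 1.3% to 10.6% change tertile (about 5 to 42 patients).
- Zero prevalence: none.

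**The case against.** The strongest reply is that Section 6 and Appendix 1 are to be read together. Step 3 of the figure already gives the exclusive rule, so x5 alone applies and the proximal LAD example scores 17.5 under both. The Appendix 1 items are multipliers rather than points, so the instruction to add does not clearly mean 2w + 5w. This stands far enough to rule out the stronger inference that occlusions *are* over-scored. The text permits that; it does not establish it, and the omitted item works the other way.

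A reader might also infer from the Version 3.0 edit that Appendix 1 is the algorithm actually programmed. The revision history says only that the occlusion item was added there; no text gives Appendix 1 precedence.

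The LAD list may be one vessel's branch of the data-entry form. Appendix 1 reads like a form, its lead-in is general, and Listing 19 is a listing of SYNTAX questions for the treated vessel. That is plausible, but nothing labels the list as an example, and Appendix 1 spells out the RCA, left main and LCX segments elsewhere.

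Finally, chronic total occlusion and STEMI are excluded, so occlusions should be few, and tertiles depend on ranks. Both points limit the consequence. Neither reconciles the two rules.

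**Conclusion.** The conflict is real and is in current text: two scoring rules are cited together as one definition and differ on three items, plus the 50% boundary. For a total occlusion the multiplier excess is 0, 2w or 5w, at most a doubling (10w against 5w), before the omitted item is taken off. For diffuse disease, 18 of 25 segments cannot score as printed.

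It would be tempting to conclude that the complexity tertiles are distorted. The documents do not support that, because the size depends on prevalences they do not give, and the simulated ranges rest wholly on assumed ones. Nor do they support a bias towards either arm: the same rule applies to both groups.

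The reach is limited to the exploratory tertile analyses, descriptive tables and sensitivity covariate analyses. The primary t-test and the secondary Wilcoxon-Mann-Whitney test do not use the score. This is a minor point, worth correcting because the correction is specific and cheap.

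**What to change.** 1. State in Section 6 that its rule governs and that Appendix 1 implements it.
2. In Appendix 1, limit the x2 item to 50-99% stenosis and state that x5 replaces x2 for a total occlusion. This also removes the difference at exactly 50%.
3. List the diffuse-disease segments for all vessels, or label the LAD list as an example.
4. Restore the non-visible-segment item where the eCRF collected it. Where it did not, state the omission as a deviation from the Section 6 score.
5. Re-derive the scores from the collected SYNTAX answers (Listing 19) before forming tertiles.

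The cost is appendix wording, a change to the derivation program and a check of what the eCRF asked. Re-derivation cannot supply points that were never collected. Recovering those would mean re-reading angiograms, which is hard to justify for an exploratory grouping, so declaring the omission is enough.
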